2nd-5th visit	
 - 1st – 4th week : Treatment session 1 per week x 4 weeks - 8th week : 1 month after treatment (2nd Data correction+Epilation)
6th visit	- 16 th week : 3 months after treatment(3 rd Data correction+Epilation)

All data will be collected using Microsoft Excel version 16.65 (Microsoft Inc, USA) and analyzed using SPSS Statistics.

Informed consent process: The study includes an informed consent (Board consent) process that allows the use of research data for future studies without the need for additional consent. . Data will be collected after this process and recorded by the investigator in a manner that subjects cannot be identified

Log book:

Provide a paper logbook to all participants to record compliance and prevent any potential co-intervention by patients or caregivers.

11. Data Analysis and Statistics

Sampling technique and Sample size: N=22 in each arm by

1-Way ANOVA Pairwise, 2-Sided Equality

$$n = 2\left(\sigma \frac{z_{1-\frac{\alpha}{2\tau}} + z_{1-\beta}}{\mu_A - \mu_B}\right)^2$$

$$1 - \beta = \Phi(z - z_{1-\alpha/(2\tau)})_+ \Phi(-z - z_{1-\alpha/(2\tau)}), z = \frac{\mu_A - \mu_B}{\sigma \sqrt{\frac{2}{n}}}$$

$$n = 2 \left(3.56 \frac{z_{1-\frac{0.05}{2\tau}} + z_{1-\beta}}{3.18 - 1.59} \right)^2$$

$$1 - \beta = \Phi(z - z_{1-\alpha/(2\tau)})_+ \Phi(-z - z_{1-\alpha/(2\tau)}), z = \frac{3.18 - 1.59}{3.56 \sqrt{\frac{2}{n}}}$$

n = Sample size (per pair) = 36, Each arm = 18, 20% drop out = 21.6 = 22 per arm

Φ = the standard Normal distribution function

Φ^{-1} = the standard Normal quantile function

α = Type I error, Significance level = 5%

β = Type II error, Power (1 - β): 80%

τ = the number of comparisons to be made = 6

Relative difference (δ) = 50% (or 0.50) by our expert opinion of minimal clinical significant difference

From previous study(28)

Standard deviation (σ) = Assume an estimated value based on available data or literature (28) = 3.56

(SD Demodex count at baseline)

$\mu_A = 3.18$

$\mu_B = 1.59$

Statistical analysis, plan, and data management

Demographic and baseline clinical characteristics will be presented as percentages for categorical data and as mean with standard deviation or median with interquartile range (IQR) for continuous data.

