For outcome ,Continuous data : Meibomian gland area ratio, Meibomian gland length and width,Meibomian gland diameter deformation index ,Meibomian gland tortuosity index, Meibomian gland signal index should be analyzed using ANOVA, while binary outcomes and ordinal data Meibomian gland dysfunction staging (severity) should be assessed using the chi-square test.

Any unavailable data will be treated as missing and will not be included in any calculations. The report will specify the percentage of missing data in each category. Statistical significance will be determined by a p-value < 0.05.

12.Ethical Consideration

The submission of the research proposal to the Institutional Review Board on Human Research at the Faculty of Medicine, Chulalongkorn University marks a pivotal step in ensuring the ethical oversight and approval of the prospective Randomized Control Trial (RCT)

Respect for Person:

Informed Consent: The principle of respect for persons underscores the importance of obtaining informed consent. Ensuring that participants have a clear understanding of the study's purpose, procedures, potential risks, and benefits is crucial.

Researchers employ transparent and comprehensive communication in the informed consent process, elucidating the randomization process, details of each intervention, and the freedom to withdraw at any point without repercussions.

Researchers will provide comprehensive information to ensure that volunteers understand the research well and make independent decisions regarding participation, without coercion or undue influence. If volunteers have legal representatives or proxies, they will be the ones reviewing the informed consent document and providing witness signatures. Researchers will seek permission from the hospital director at Chulalongkorn Hospital and will anonymize data using codes without disclosing patients' names, surnames, or hospital identification numbers.

Beneficence/Non-maleficence:

Risk-Benefit Assessment: Ethical research necessitates a careful evaluation of potential benefits against risks. Researchers must strive to maximize the positive outcomes of the study while minimizing any harm to participants.

Continuous monitoring of the interventions for unexpected risks and a commitment to modify or halt the trial if harms outweigh benefits are imperative to uphold the principles of beneficence and non-maleficence.

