- Patient Adherence: The effectiveness of interventions depends on patient adherence to treatment protocols. Challenges may arise if patients perceive the procedures as burdensome or experience difficulties maintaining compliance.

6. Limitations of AI Technology

- Algorithm Performance: AI-driven meibomian gland analysis is dependent on the quality of algorithms and training data. Variability in clinical conditions and diverse populations may impact the accuracy and effectiveness of AI models.

7. Integrating AI Insights into Clinical Practice

- Clinical Implementation: Translating AI-supported research findings into practical clinical guidelines and integrating them into routine practice requires extensive validation. Additional verification and refinement of study results may be necessary before AI-driven approaches can be widely adopted in clinical settings.

15. Risk and Investigator's Responsibility

1. Patient Privacy Protection:

Risk: The collection of sensitive health information necessitates the protection of patient privacy. Investigator's Responsibility: The investigator must adhere to data protection regulations, implement robust anonymization practices, and establish secure data storage and transmission procedures to safeguard patient privacy.

2. Participant Discomfort during Interventions:

Risk: Participants undergoing Photobiomodulation (LLLT) and Intense Pulsed Light (IPL) therapies may experience mild discomfort or temporary side effects.

Investigator's Responsibility: The investigator must thoroughly explain potential discomfort during the informed consent process and promptly address any participant concerns or adverse reactions.

3. Selective Reporting Bias:

Risk: There is a risk of selective reporting bias.

Investigator's Responsibility: The investigator must commit to transparently reporting all outcomes, fostering an unbiased and comprehensive understanding of the interventions' efficacy.

4. Bias and Accuracy in AI Analysis

Risk: AI models may have inherent biases or limitations that affect the accuracy of meibomian gland analysis, potentially leading to incorrect diagnoses or assessments.

Investigator's Responsibility: Researchers must rigorously monitor and evaluate the performance of AI systems, actively identifying and addressing biases or errors to ensure the reliability and credibility of study outcomes.

16. Timeline

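### Missing counts are simply left out at each visit although 20% dropout is expected, which can bias the week-8 and week-16 comparisons in either direction if dropout relates to response and differs between arms

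*Combined protocol and SAP*

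**What the plan says.** All references are to the combined protocol and SAP.

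- **Missing data** (section 11, statistical analysis): "Any unavailable data will be treated as missing and will not be included in any calculations". The next sentence adds: "The report will specify the percentage of missing data in each category". What a category is, and whether arm is one, is not said.
- **Expected dropout** (section 11, sample size): "Each arm = 18, 20% drop out = 21.6 = 22 per arm".
- **Counts taken** (section 10): baseline, week 8 (primary) and week 16 (secondary).
- **Tests named** (section 11): ANOVA for the meibography measures and chi-square for binary and ordinal outcomes. The sample-size method implies one-way ANOVA for the mite count. No baseline term, earlier-visit term or repeated-measures model appears.
- **Stopping and leaving**: section 12 gives participants "the freedom to withdraw at any point without repercussions". Section 15 says that patients receiving light therapy "may experience mild discomfort or temporary side effects". Section 14, item 5 says: "Challenges may arise if patients perceive the procedures as burdensome or experience difficulties maintaining compliance".
- **Compliance**: section 4.4 says that moderate and poor compliers will be excluded. The exclusion criteria in section 9 list poor compliance with the scrubs only. Neither says whether this applies before or after randomisation.

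The document names no analysis set, imputation, missing-data assumption or sensitivity analysis.

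**The concern.** A mean over the patients who happen to be observed estimates the randomised arm's mean only if being missing is unrelated to the count. If poor responders leave an active arm, that arm looks better than it was. If they leave the sham arm, the sham arm looks better and a real effect shrinks. Raising 18 to 22 per arm protects precision but does nothing about this.

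Two gaps add to the risk. The plan does not separate stopping the light sessions or scrubs from leaving follow-up, so a patient who stops treatment may also be lost to the week-8 and week-16 epilations. And the compliance exclusion, if applied after randomisation, would remove patients by their behaviour on treatment and act like informative dropout.

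The rule also discards information. A patient seen at week 8 and lost afterwards has a week-8 count that helps predict week 16, and the named tests make no use of it.

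**Working it through.** **Inputs from the plan (section 11).** Means 3.18 and 1.59, so a difference of 1.59; SD 3.56; dropout 20%; 18 evaluable and 22 randomised per arm. **Assumed:** the dropout mechanism, the rates by arm and the between-visit correlation, because the plan gives none of them.

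**1. The plan's dropout step.** 18 × 1.2 = 21.6, rounded up to 22: reproduced. With 20% lost, 22 × 0.8 = 17.6 remain, just under 18. (The 18 itself does not follow from the plan's formula, which gives 121.4, so 122 per arm. That is a separate and larger problem.)

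**2. Bias by arithmetic.** Let d be the dropout fraction in an arm and D the excess mean count of its dropouts over its completers. The arm's true mean is the completer mean + d × D. The error in the control-minus-active difference is therefore

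bias = d(active) × D(active) − d(control) × D(control).

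For example, if 80% of an active arm stay with mean 1.59 and 20% leave with mean 3.18, the true mean is 0.8 × 1.59 + 0.2 × 3.18 = 1.908. The rule reports 1.59. The error is 0.318, and 0.318 / 1.59 = 20% of the planned difference.

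With d = 20% and dropout informative in the active arm only:

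| D (mites) | 0.20 × D | Share of 1.59 |
|---|---|---|
| 0.5 | 0.10 | 6% |
| 1.0 | 0.20 | 13% |
| 1.78 | 0.36 | 22% |
| 3.56 | 0.71 | 45% |

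With the same D and 20% dropout in both arms, the bias is 0. With the same D and 20% against 10%, it is 0.10 × D, or 0.05 to 0.36 (3% to 22%).

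**3. Week 16, loss driven by the week-8 count (simulation).** Counts are normal with SD 3.56 and the plan's means at both visits. Dropout after week 8 averages 20% in each arm. In the informative arm its log-odds rise by 1 per SD of the week-8 count; in the other arm it is random. The true difference is 1.59.

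| Correlation, week 8 to 16 | Informative in control only | Informative in active only | Same within-arm mechanism in both |
|---|---|---|---|
| 0.3 | 1.40 | 1.78 | 1.59 |
| 0.5 | 1.28 | 1.90 | 1.59 |
| 0.7 | 1.16 | 2.02 | 1.59 |

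A weaker slope of 0.5 per SD gives about 1.35 to 1.49 and 1.69 to 1.83 in the one-arm cases. If dropout is instead the same function of the absolute count in both arms, the control arm loses more patients (about 22% to 23% against 17% to 18%) and the bias is −1% to −9%. Regressing week 16 on week 8 brings the one-arm results back to about 1.59. It must, because dropout was generated from the week-8 count.

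**4. Week 8, loss driven by the week-8 outcome itself, active arm only.** Same slope of 1 per SD. The complete-case difference is about 2.20 against 1.59. Adjusting for baseline gives only 2.15, 2.06 and 1.92 at baseline correlations of 0.3, 0.5 and 0.7.

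Real mite counts are skewed and cannot be negative, so these figures show the order of size only.

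**The case against.** The rule excludes unavailable data, not patients. A reader might infer that someone who misses one visit is removed from every calculation. The plain wording does not say so: a patient seen at week 8 still counts at week 8. Listwise deletion is not ruled out, but it is not stated either.

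A reader might also infer that the plan itself predicts arm-dependent dropout. It does not. Section 15 lists discomfort as a risk to explain at consent and does not tie it to withdrawal. Section 14, item 5 is about adherence. Much of the burden is common to all arms, since everyone has compresses and scrubs for 90 days and the sham groups attend sham sessions. Response-related dropout is plausible here, but it is an assumption.

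The size depends on asymmetry between arms. With a common mechanism it is nil or small. Even 0.32 is only about 0.27 of the standard error of a pairwise difference at 18 per arm (3.56 × √(2/18) = 1.19).

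A repeated-measures model is also no cure for the primary outcome. Light sessions fall in weeks 1 to 4, so a patient who leaves during them has no post-baseline count and does not enter the model. Step 4 shows how little baseline adjustment recovers.

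All of this stands. It limits the size and certainty of the bias and shows that a model alone is not enough. It does not supply a rule for patients who stop treatment, a use for counts already taken, or any check on the omission of missing values.

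**Conclusion.** The point holds as a conditional one. The plan uses a complete-case analysis by visit, expects 20% dropout, and has nothing that would reveal or limit bias if dropout depends on response and differs between arms. Under assumed one-arm mechanisms, the week-16 difference of 1.59 becomes about 1.2 to 1.4 or 1.8 to 2.0. With the same mechanism in both arms, the bias is about zero. At week 8, outcome-related loss could matter as much, and earlier data would correct little of it.

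The documents do not support saying that the contrasts will be biased, that the direction is known, or that patients with a missed visit lose their observed data. The loss of information concerns mainly week 16; at week 8 only the baseline count is available. The figures rest on assumed mechanisms, correlations and normality, and on the plan's SD. A smaller SD gives a smaller bias.

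**What to change.** Replace the missing-data sentence in section 11 and align sections 4.4, 9 and 10 with it:

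1. **Follow-up.** Patients who stop light sessions or scrubs and have not withdrawn consent stay on the scheduled week-8 and week-16 epilations and are analysed as randomised. Reconcile this with the compliance exclusion in sections 4.4 and 9, which differ from each other, so that it is not used to remove patients after randomisation.
2. **Main analysis.** Fit one repeated-measures model to the week-8 and week-16 counts, including the baseline count, using all randomised patients with any post-baseline count. State that an observed visit is kept when another is missing.
3. **Reporting.** Give missingness and its reasons by arm and visit.
4. **Sensitivity analysis.** Repeat the primary week-8 comparison over a range of assumed values for missing counts, allowed to differ between arms, with baseline carried forward as one scenario. This shows how robust the result is. It does not test the missing-at-random assumption.

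**Cost.** Wording changes, one further model in SPSS, which the plan already names, and a short sensitivity table. No visits or epilations are added to the schedule. The downside is a little more analysis work and a main model that relies on data being missing at random.

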A score of 100 corresponds to complete disability (a response of "all of the time" to all questions answered), while a score of 0 corresponds to no disability (a response of "none of the time" to all questions answered). Therefore, change from baseline of -12.5 corresponds to an improvement by at least one category in half of the questions answered.					
Subscale Scoring					
Subscales scores are computed similarly with only the questions from each subscale used to generate its own score. Therefore, any subscales analyzed separately would also have a maximum possible score of 100.					
The three subscales (vision-related function, ocular symptoms and environmental triggers) are broken out as follows:					
Subscale	Questions				
Vision-Related Function	4, 5, 6, 7, 8, 9				
Ocular Symptoms	1, 2, 3				
Environmental Triggers	10, 11, 12				

Meibum Quality.

Meibum Expressibility.

[figure not shown]
Telangiectasia grading: 0-3

3.Surface Staining: NEI Grading System.

4.Lipid Layer Thickness by LIPIVIEW

5.Noninvasive break-up time (NIBUT), tear meniscus height (TMH) , % Meibomian Gland Loss (MGL) by Keratograph 5M (OCULUS, Germany)

6.Corrected one times baseline , including BCVA, IOP.

7. After complete datacorrection : Meibography images will be masked and analyzed using an AI-assisted program to assess the following:

- Meibomian gland dysfunction staging (severity): MGD severity level and scored with 1-5 according to the 2011 MGD workshop (27) (Figure1)
- Meibomian gland area ratio: The proportion of the total visible meibomian gland area to the overall tarsal area in the eyelid
- Meibomian gland length: The linear measurement from the proximal to distal end of a meibomian gland, reflecting its elongation or shortening due to disease.
- Meibomian gland width: The horizontal width of individual meibomian glands, which helps assess gland atrophy or hypertrophy.

- Meibomian gland diameter deformation index: A metric for measuring irregularities in the shape and thickness of the glands, indicating glandular structural deformation.
- Meibomian gland tortuosity index: A measure of the curvature or twisting of the meibomian glands, used to assess changes in gland architecture.

Meibomian gland signal index: The intensity or brightness of the meibomian gland signal in meibography images, indicating gland density and activity

Visiting schedule:

1st visit	- Before treatment within 0-14 days (1 st Data correction+Epilation)

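### Seventeen or eighteen secondary and AI outcomes share an unqualified p < 0.05 rule, with no testing order, correction or supportive label

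*Combined protocol and SAP*

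**What the plan says.** The statistical analysis part of section 11 closes with "Statistical significance will be determined by a p-value < 0.05". The sentence is not limited to the primary outcome, and nothing nearby gives an order of testing, an adjustment or a supportive status for any outcome.

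One primary outcome is named in sections 10 and 12: the Demodex count 30 days after the end of treatment (week 8). Section 10 then lists the secondary outcomes, ending with item 7: "Meibography images will be masked and analyzed using an AI-assisted program to assess the following". The visit schedule in section 10 collects data at weeks 8 and 16, but only the mite count is tied to a particular visit.

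Multiplicity appears once, in the sample-size part of section 11. That calculation is headed "1-Way ANOVA Pairwise, 2-Sided Equality" and uses "τ = the number of comparisons to be made = 6". It concerns the six pairs of arms for the mite count.

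Section 15 recognises selective reporting as a risk and answers it with "The investigator must commit to transparently reporting all outcomes".

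**The concern.** Many outcomes judged separately at 0.05 will tend to produce some nominally significant results even if the treatments do nothing. The plan gives no way to tell such a result from a finding it set out to confirm. Section 13 expects the results to inform clinicians' choice among light-based treatments, so a stray significant secondary could be read as evidence for one of them.

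The documents also disagree on which outcomes count. The outcomes that section 11 names for testing are the six AI gland measures and MGD staging, whereas the Outcomes list in section 12 omits those six measures. MGD stage itself appears twice in section 10, once as item 2 and once among the AI readings. With no main visit named for any secondary outcome other than the mite count, the visit could also be chosen after the data are seen.

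**Working it through.** **Plan's own figure.** The plan states no family-wise error rate, so there is none to reproduce. The one stated result that involves multiplicity is the sample size. The plan's formula with α = 0.05, τ = 6, 80% power, SD 3.56 and difference 1.59 gives 2 × (3.56 × (2.638 + 0.842) / 1.59)² ≈ 121.4, so 122 per arm against the stated 18. That is a separate matter, and the error rates below do not depend on it.

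**Counting outcomes (section 10).**
- Items 1 to 5: week-16 mite count, MGD stage, OSDI, meibum quality, meibum expressibility, telangiectasia, surface staining, lipid layer thickness, NIBUT, TMH and percentage gland loss. That is 11.
- Item 7, AI readings: area ratio, length, width, diameter deformation, tortuosity and signal index. That is 6.
- Total 11 + 6 = 17, or 18 if the AI-derived MGD stage is separate from item 2. BCVA and IOP are taken once at baseline and are not counted.

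**Independent tests, all nulls true, one test per outcome.** Chance of at least one p < 0.05 = 1 − 0.95^k.
- k = 17: 1 − 0.95^17 = 0.582
- k = 18: 1 − 0.95^18 = 0.603
- Expected false positives: 17 × 0.05 = 0.85, or 18 × 0.05 = 0.90. These two figures do not depend on correlation.

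**Correlated outcomes.** The documents give no correlations, so these are assumptions. Four-arm one-way ANOVAs were simulated under the global null with 18 or 22 per arm, equal correlation between outcomes and 4,000 to 6,000 runs.

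| Assumed correlation | 17 outcomes | 18 outcomes |
|---|---|---|
| 0 (formula) | 58% | 60% |
| 0.3 | 50–51% | 51% |
| 0.5 | 40–42% | 42% |
| 0.7 | 29–30% | 30% |
| 0.9 | 16% | 16% |

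**More tests.** Testing both visits, or adding unadjusted pairwise contrasts to the overall test, can only raise these figures. The extra tests add ways to reach p < 0.05 and remove none.

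**Direction.** An overall ANOVA or chi-square test has no direction. For 17 outcomes at one visit, the chance of a false result in the favourable direction is:
- 1 − 0.975^17 = 0.350, if each outcome has one independent two-sided test;
- about 29%, 23–24% and 19–20% at correlations 0, 0.3 and 0.5, if a significant ANOVA must come with an active arm better than control;
- about 66–68%, 49–51% and 39–40% at the same correlations, if each active arm is compared with control, unadjusted and without a preceding ANOVA.

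**What control would require.** Bonferroni over 17 outcomes sets 0.05 / 17 = 0.0029 per test, for a family rate of 1 − (1 − 0.05/17)^17 = 4.9% if independent.

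**The case against.** The plan names one primary outcome at one time and calls the rest secondary. It nowhere says that success of the trial rests on a secondary. Section 15 promises that all outcomes will be reported, which lets a reader see how many were tested. Both points stand, but neither controls the error rate or says how a secondary p-value below 0.05 is to be read.

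The outcomes also overlap. The severity table in Figure 1 grades MGD by symptoms and OSDI, meibum quality and gland loss; the AI area ratio is close to the complement of percentage gland loss; and the AI measures come from the same images. Independence is therefore an upper reference, not a realistic case. In addition, OSDI, meibum quality, expressibility and telangiectasia stand unnumbered beneath MGD staging in section 10. If they were only components of it, the count would be 13 and the independent figure 1 − 0.95^13 = 0.487. The list of dependent variables under the conceptual framework names each separately, which supports 17.

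Three stronger readings are tempting, and the documents do not support them.
- A reader might infer that a false positive is more likely than not. That needs at least 14 independent tests with every null true (1 − 0.95^14 = 0.512), or extra tests. At correlation 0.5 with one test per outcome the figure is about 41%.
- A reader might infer that the false positive would be a benefit. The tests named in section 11 have no direction.
- A reader might double the tests for the two visits, giving 16 × 2 + 1 = 33 and 1 − 0.95^33 = 0.816. No section says that each outcome is tested separately at each visit.

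**Conclusion.** The point holds as a defect of the significance rule. Seventeen or eighteen outcomes share an unqualified 0.05 threshold, and the plan's only multiplicity term stops at the sample size. With one test per outcome and all nulls true, the chance of at least one false positive is 58% to 60% if independent and about 51%, 41% and 30% at assumed correlations of 0.3, 0.5 and 0.7. Even at 0.9 it is about 16%, three times the nominal 5%. The exact size depends on correlations that the documents do not give; the conclusion that it is well above 5% does not. The mismatch between the outcome lists does not enter this calculation, but it leaves unclear which results could support a claim.

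**What to change.** In section 11, replace the blanket rule as follows.
- Confine claims of statistical significance to the week-8 Demodex count, with its pairwise comparisons held at 5% overall, in line with τ = 6 (for example 0.05 / 6 = 0.0083 per pair).
- Label all secondary and AI outcomes as supportive or exploratory. Report them as between-group estimates with 95% confidence intervals and no significance label.
- Name one main visit for each outcome.
- Use one identical outcome list in sections 10, 11 and 12, and state whether MGD stage is the clinical or the AI-derived version.

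If the sponsor wants a confirmatory secondary, it should be named with its visit under a stated multiplicity rule that defines success on the primary. A rule that tests it only after the primary succeeds has a price. On the plan's inputs, power for a given pair at 18 per arm is 9.7% with τ = 6 (z = 1.59 / (3.56 × √(2/18)) = 1.34, against a critical value of 2.638), so the gate would often stay closed.

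The main change is to wording and needs no new data, visits or patients. Its cost is that fewer outcomes can be called statistically significant.
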